14.5 MISSING DATA

The underlying mechanism of missing data and reasons for missing-ness will be scrutinised to assess the assumption of missing at random. Missing outcome data may be imputed dependent on level of missing-ness. Details on the model and method used for missing data will be specified within the SAP, finalised before analysis.

14.6 SAMPLE SIZE

The trial design, sample size and power calculations are informed by the previous LaCeS feasibility trial [10, 31], based upon a superiority hypothesis for the primary outcome measure. Secondary outcome measures are not powered. The incidence of 30-day complication rates was estimated in LaCeS feasibility as 41.9% (95% CI 24.6%, 60.9%) in the open surgery group (31 pts). Based on clinical consensus of the applicants, an absolute reduction of at least 15% is considered achievable and represents the minimum clinically relevant difference required to change practice.

512 patients are required in total to detect a 15% absolute reduction in the incidence of 30day complications with 90% power and a 5% 2-sided significance level, using a two-group continuity corrected chi-squared test of equal proportions. This assumes an incidence of 30day complications of 45% in the open surgery arm, based on results of LaCeS feasibility, literature [2, 3] and clinical opinion, and accounts for a 10% drop-out, as observed in LaCeS feasibility (nQuery Advisor v7.0). At least 88% power will be achieved to detect a 15% absolute reduction should the incidence of complications in the open surgery arm be higher than observed in LaCeS feasibility (up to 60%). The external, independent Data Monitoring Committee will monitor the underlying sample size assumptions at the end of the pilot phase.

15 HEALTH ECONOMIC EVALUATION

The economic evaluation will compare laparoscopic with open colorectal surgery adhering to the NICE reference case [32]. The primary end-point will be cost per incremental quality-adjusted life year (QALY) and the perspective that of the health and personal social service (PSS) provider. A supplementary analysis will adopt a wider perspective and incorporate patient and carer costs. We will report incremental cost-effectiveness ratios (ICERs) [33] at trial end (12 months) however the primary end-point will be based on lifetime expected costs and outcomes generated from a de novo decision analytic model. Our analysis will be detailed in a Health Economic Analysis Plan (HEAP) and will mirror the approach of the statistical analysis plan and analyse the intention to treat sample (based on randomisation) but also conduct supplementary analysis evaluating actual surgery received (open, laparoscopic or laparoscopic converted to open surgery).

Costs and outcomes

Resource use and utility data will be captured in the trial at baseline and each follow-up assessment point.

We will conduct a micro-costing of the interventions based on CRF data on theatre time and staff involvement (staff number, type and grade). Data on hospital visits (inpatient and outpatient) and length of stay up to 12 months will be collected using CRFs which will also capture detail on ward type and whether critical care was required. Primary (e.g. GP contact and district nurse visits) and social care (e.g. social worker and home help) resource use will be captured on a patient completed form. This strategy proved successful in the feasibility study and limited missing data. This form will also capture data on patient and carer costs incurred in the receipt of health care. Unit costs will be taken from the PSSRU report, NHS Reference costs and participating trust finance departments.

Utility will be captured using the EQ-5D-5L [15]. Currently, NICE advise the use of a published (EQ-5D-5L to EQ-5D-3L) mapping algorithm to generate the utility index from the EQ-5D-5L [34] [35]. However, a new valuation study is on-going [36]and we will use the new UK valuation tariff when this is available, providing the results are valid and robust. A supplementary analysis will explore basing quality-adjustment based on the SF-6D (derived from the SF-12) [37]. We will use an area under the curve approach to estimating 12 months QALYs.

Trial analysis

We will use seemingly unrelated regression models to analyse cost and QALY data during the trial follow-up, allowing us to account for the correlation between the two outcomes. Where appropriate, we will mirror the statistical approach to incorporating control variables and adjust for the specified minimisation factors. We will also adjust for any imbalance in baseline costs and utility if necessary. The analysis will account for clustering at surgeon level and employ a multi-level model [38]. Parametric or non-parametric (i.e. bootstrapping) methods will be used to characterise the sampling uncertainty present with simulations plotted on a cost-effectiveness plane and cost-effectiveness acceptability curves.

We will assess the type and degree of missing data and evaluate whether the assumption of missing at random (MAR) holds [39]. If that is the case, multiple imputation will be used to impute missing data. Should MAR not hold we will explore the impact of alternative assumptions [40].

Decision model

As the benefits of the interventions are expected to extend beyond the trial follow-up period, we will develop a decision-analytic model to estimate future costs and benefits following best practice [41]. The model type and structure will be agreed after consultation with clinical experts and patients and a review of existing models in the area. The model development process will determine whether one decision model will be sufficient or if other sub-models are required to capture relevant long-term impacts of the different colorectal pathologies (e.g. disease free vs. recurrence health states in cancer [42] and specific long term complications in inflammatory bowel disease). We will develop a model outline document distinct from the HEAP and in collaboration with the team to detail the model structure, parameters and analytical approach.

Twelve month cumulative cost and QALY data (and related variance) generated from the trial will feed into the model at initiation. We will use trial data and targeted literature reviews to derive health state parameters and use NELA to derive additional parameters of interest (e.g. relating to learning effects). The model will enable the calculation of discounted lifetime ICERs and estimates of net monetary benefit (NMB). We will assume a cost-effectiveness threshold of £20,000 per QALY gained. We will conduct extensive deterministic one-way and scenario sensitivity analyses which will allow us to explore, for example, the impact of surgeon learning curves and alternative implementation scenarios on cost-effectiveness. Monte Carlo simulations using draws from parameter distributions will allow a probabilistic sensitivity analysis capturing total parameter uncertainty in the model. Results from this will be presented in the form of cost-effectiveness planes, NMB distributions and cost-effectiveness acceptability frontiers [43].

Costs and benefits post 12 months will be discounted at a rate of 3.5% per annum as per NICE guidance. All reporting of results will conform to published guidelines [44] [45].

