9.4.2. RANDOMISATION PROCESS

Following confirmation of written informed consent and eligibility, patients will be randomised into the trial by an authorised member of staff at the trial site. Participant-completed baseline questionnaires (SF-12[®], EQ-5D-5L[™] and a Health Economics Questionnaire, see section 11.5) should be completed after consent has been obtained and prior to randomisation, however, where this is not possible these must be completed before the participant is informed of their randomised treatment allocation.

Randomisation will be performed centrally using the CTRU automated 24-hour randomisation system which can be accessed via the web or telephone. User ID codes and personal identification numbers (PINs), provided by the CTRU, will be required to access the randomisation system.

The following information will be required at randomisation:

- Patient details, including initials, date of birth, height and weight
- Name and code of the research site
- Name of the person making the randomisation
- Confirmation of eligibility
- Confirmation of written informed consent
- Minimisation factors (see section 9.4.3)

The randomisation system will allocate participants a unique 5 digit trial number and inform of the randomised operation for that participant (laparoscopic or open surgery).

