11 DATA COLLECTION

Participating research sites will be expected to maintain a file of essential trial documentation (ISF), which will be provided by the CTRU, and keep copies of all completed CRFs for the trial. Paper CRFs, eCRFs and participant-completed questionnaires will contain the participant's unique trial number, date of birth, and initials. Clinical data will be collected at baseline, operation, hospital discharge and at 6 weeks, 90 days, 6 months and 12 months post-operation; participant-completed data will be collected at baseline and at 30 days, 90 days, 6 months, 9 months and 12 months post-operation.

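### Baseline utility should be a fixed covariate in the QALY model, not one added only if imbalance makes it necessary

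*Protocol*

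**What the plan says.** The within-trial economic model is set out in protocol section 15, under trial analysis: "We will use seemingly unrelated regression models to analyse cost and QALY data during the trial follow-up". Covariates come in two sentences. The first covers the minimisation factors: "Where appropriate, we will mirror the statistical approach to incorporating control variables and adjust for the specified minimisation factors". The second covers baseline values: "We will also adjust for any imbalance in baseline costs and utility if necessary". No test, threshold or other criterion says what counts as imbalance or when adjustment becomes necessary.

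The minimisation factors in section 9.4.3 are surgeon, age, BMI, ASA status, pathology and intended procedure. None is a utility or a cost.

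The baseline utility exists. Section 15 states: "Resource use and utility data will be captured in the trial at baseline and each follow-up assessment point". Section 9.4.2 says that the baseline questionnaires "should be completed after consent has been obtained and prior to randomisation", with a fallback that they are completed before the participant learns the allocation. On QALYs, section 15 says: "We will use an area under the curve approach to estimating 12 months QALYs". The time points are in section 11: "participant-completed data will be collected at baseline and at 30 days, 90 days, 6 months, 9 months and 12 months post-operation".

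The within-trial result is carried forward: "Twelve month cumulative cost and QALY data (and related variance) generated from the trial will feed into the model at initiation". Section 15 makes the lifetime model the basis of the primary economic end-point and defers detail to a Health Economic Analysis Plan (HEAP), which is not at hand.

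**The concern.** After randomisation, any baseline difference between the arms is due to chance, so observed imbalance is not what makes a baseline covariate worth having. Its value lies in how well it predicts the outcome. Baseline utility is the first point of the area under the curve, and later utilities in the same patient are likely to be correlated with it. A model containing it therefore estimates the QALY difference with less residual variance even when the arms look alike.

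A rule that first looks at baseline and then decides has two weaknesses. It leaves the choice of model open until the baseline data by arm have been seen. It also drops the covariate in exactly the trials where the arms look balanced, although the precision is available there too. The incremental QALY is the denominator of the ICER, and its variance is passed to the lifetime model, so both weaknesses carry through to the probabilistic results.

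Sections 14.3 and 14.4 adjust the clinical models for all minimisation factors without any look at balance, and section 15 says that the economic analysis will follow the statistical plan's approach. The baseline sentence departs from that principle.

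**Working it through.** **1. The plan's own figure.** The protocol gives no figure for the QALY analysis. Its only sample size is 512, for the primary outcome (section 14.6: 45% against 30%, 90% power, two-sided 5%, continuity-corrected chi-squared test, 10% drop-out).
- Uncorrected n per arm = [1.96·√(2·0.375·0.625) + 1.2816·√(0.45·0.55 + 0.30·0.70)]² / 0.15² = 216.8.
- Corrected n per arm = (216.8/4)·[1 + √(1 + 4/(216.8·0.15))]² = 230, so 460 in total.
- 460/0.90 = 511.1, rounded up to 512. The figure reproduces, and this point does not touch it.

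Below, 460 analysed (230 per arm) is borrowed as a working number. The number with usable QALY data is not stated.

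**2. Direct weight of baseline in the QALY.** With the trapezium rule and utilities at 0, 30, 90, 182.5, 273.75 and 365 days, the weights are 0.041, 0.123, 0.209, 0.252, 0.250 and 0.125. Baseline has (30/2)/365 = 0.041. A baseline difference of 0.05 therefore adds 0.05 × 0.041 ≈ 0.002 QALY directly. Almost all of any gain from adjustment must come through correlation with later utilities.

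**3. Gain from always adjusting.** Let ρ be the partial correlation of baseline utility with the 12-month QALY, given the minimisation factors already in the model. The documents give no value, so ρ is assumed. The variance of the adjusted difference is (1 − ρ²) times that of the difference without baseline utility. The equivalent in extra patients is 460/(1 − ρ²) − 460.

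| ρ (assumed) | Variance reduction (ρ²) | Extra patients, from 460 |
|---|---|---|
| 0.1 | 1% | 5 |
| 0.2 | 4% | 19 |
| 0.3 | 9% | 45 |
| 0.4 | 16% | 88 |
| 0.5 | 25% | 153 |

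**4. What a conditional rule would recover.** The protocol gives no trigger, so several were assumed. The simulation used 20,000 trials of 230 per arm, with standardised normal baseline and outcome, no treatment effect and no other covariates.

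| Assumed trigger | Trials in which adjustment occurs |
|---|---|
| Baseline p < 0.05 | 5% |
| Baseline p < 0.10 | 10% |
| Baseline p < 0.20 | 20% |
| Standardised difference > 0.2 | 3% |
| Standardised difference > 0.1 | 28% |
| Standardised difference > 0.05 | 59% |

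| ρ | Variance reduction, adjust if p < 0.05 | Adjust if p < 0.20 | Always adjust |
|---|---|---|---|
| 0.2 | 1% | 3% | 4% |
| 0.3 | 2% | 6% | 9% |
| 0.5 | 7% | 17% | 25% |

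**5. Error rate under the conditional rule.** Across ρ of 0.2, 0.3 and 0.5 and the three p-value triggers, the rejection rate under no effect was 3.8% to 4.9% against a nominal 5%. The mild conservatism has a simple cause. When no adjustment is triggered, the reported standard error still allows for large baseline differences, although the rule has just excluded them.

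**The case against.** The strongest reply is that the covariates of an economic regression are commonly settled in the HEAP. That plan could fix baseline adjustment before any data are seen, and the sentence does not forbid it. This stands in part: the documents do not show that the model will in fact be picked after looking at the data. But the protocol is not silent here. It states a rule, and a HEAP that followed the rule as written would keep it conditional.

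Several stronger readings are tempting, and the documents do not support them.
- A reader might infer that the intervals would be invalid or the error rate inflated. The trigger depends on baseline variables, not the outcome, and the simulation shows no inflation.
- A reader might infer that chance imbalance would materially bias the QALY difference. The sentence itself promises to deal with imbalance, and the direct weight of baseline is only 0.041.
- A reader might infer that the trial would usually go unadjusted. With no trigger defined, the frequency runs from 3% to 59% across the rules tried, and someone who took the word any literally would adjust nearly always.
- A reader might expect a large gain. Baseline is completed by acutely ill patients awaiting urgent surgery, so its correlation with later utility may be low. The planned minimisation factors may already account for part of it, which is why the partial correlation is the relevant one.

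It is also fair to say that no gain has been shown for baseline cost.

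**Conclusion.** The point holds as a matter of method. The stated rule uses the wrong trigger, has no criterion, and can give up precision in the incremental QALY that a scheduled baseline measurement would supply. The harm is lost precision, slightly conservative inference and avoidable analyst discretion.

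The size cannot be derived from the documents. It rests on an assumed partial correlation, and the lower rows of the table in the working are plausible here, so the gain may be no more than a few per cent. The comparison with a conditional rule rests in addition on an assumed trigger and on a simplified two-arm simulation. The point concerns the economic analysis and its inputs to the lifetime model only.

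**What to change.** Replace the conditional sentence in protocol section 15, and carry the same wording into the HEAP, with text such as: *Baseline EQ-5D-5L utility will be included as a covariate in the QALY equation in all analyses, irrespective of observed imbalance.* Treat baseline cost the same way in the cost equation, for consistency rather than for a demonstrated gain. Handle missing baseline values within the multiple imputation that section 15 already plans under missing at random.

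The cost is one degree of freedom per equation. In a simple comparison of 460 patients the residual degrees of freedom go from 458 to 457, so the loss is negligible even if the correlation is near zero. No new data, visits or patients are needed.

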16 TRIAL MONITORING

Trial supervision will be established according to the principles of GCP and in-line with the NHS UK Policy Framework for Health and Social Care. This will include establishment of a core Project Team, Trial Management Group (TMG), an independent TSC and independent DMEC. A Trial Monitoring Plan will be developed based on the trial risk assessment; this may include site monitoring.

Protocol Version 2.0_19th July 2023 ISRCTN38815804 IRAS Project ID: 291081 REC Reference: 21/NW/0303

16.1 TRIAL STEERING COMMITTEE (TSC) & DATA MONITORING AND ETHICS COMMITTEE (DMEC)

An independent DMEC will be appointed to review the safety and ethics of the trial, alongside trial progress and overall direction as overseen by the TSC. Detailed un-blinded reports will be prepared by the CTRU for the DMEC at approximately yearly intervals.

The DMEC will report to the TSC, who will remain blind and will have overall external oversight of the trial (ensuring regular reports to the NIHR Health Technology Assessment (HTA) Programme). Further details about the responsibilities of each committee can be found in section 20.1.

16.2 DATA MONITORING

Data will be monitored for quality and completeness by the CTRU. Missing data will be chased until they are received, until confirmed as not available, or until the trial is at analysis. The CTRU or Sponsor will reserve the right to intermittently conduct source data verification (SDV) exercises on a sample of participants, which will be carried out by staff from the CTRU or Sponsor. SDV will involve direct access to participant medical notes at the participating research sites and the ongoing central collection of copies of consent forms and other relevant investigation reports.

A Trial Monitoring Plan will be developed.

16.3 CLINICAL GOVERNANCE ISSUES

To ensure responsibility and accountability for the overall quality of care received by participants during the trial period, clinical governance issues pertaining to all aspects of routine management will be brought to the attention of the TSC and, where applicable, to individual research sites.

17 QUALITY ASSURANCE AND ETHICAL CONSIDERATIONS

17.1 QUALITY ASSURANCE

The trial will be conducted in accordance with the principles of GCP in clinical trials, the NHS UK Policy Framework for Health and Social Care and through adherence to CTRU SOPs.

17.2 SERIOUS BREACHES

The CTRU and Sponsor have systems in place to ensure that serious breaches of GCP or the trial protocol are picked up and reported. Investigators are required to **immediately** notify the CTRU of a serious breach (as defined in the latest version of the HRA SOP) that they become aware of. A 'serious breach' is defined as a breach of the protocol or of the conditions or principles of GCP (or equivalent standards for conduct of non-CTIMPs) which is likely to affect to a significant degree-

- a) the safety or physical or mental integrity of the trial subjects, or
- b) the scientific value of the research

In the event of doubt or for further information, the Investigator should contact the Senior Trial Manager at the CTRU.

17.3 ETHICAL CONSIDERATIONS

The trial will be performed in accordance with the recommendations guiding physicians in biomedical research involving human subjects adopted by the 18th World Medical Assembly, Helsinki, Finland, 1964, amended at the 64th World Medical Association General Assembly, Fortaleza, Brazil, October 2013. Informed written consent will be obtained from the participants prior to randomisation into the trial. The right of a patient to refuse participation without giving reasons must be respected. The participant must remain free to withdraw at any time from the trial without giving reasons and without prejudicing his/her further treatment.

Ethical approval will be sought through the Health Research Authority (HRA). The trial will be submitted to and approved by a REC, the HRA and the appropriate Site Specific Assessor for each participating research site prior to entering participants into the trial. The CTRU will provide the REC with a copy of the final protocol, participant information sheets, consent forms and all other relevant trial documentation.

18 INFORMATION GOVERNANCE AND CONFIDENTIALITY

The University of Leeds is the data controller for the trial. The University of Leeds and the University of Hull will be joint data controllers for the data relating to the qualitative sub-study. Participating sites will be data processors for any trial data processing (while remaining data controllers of data processing required for patient care).

All data processing for the trial will be in accordance with the 2018 Data Protection Act. Personal data will be processed under a lawful basis of 'task in the public interest' (GDPR Article 6, 1(e)) and special categories of personal data (in this case, data about health, racial or ethnic origin and genetic data) will be processed for scientific research purposes (GDPR Article 9, 2(j)).

All trial participants (and any patients considered for the trial) are provided with detailed information about how their data will be processed before any trial data processing. Any material changes to how data will be processed will be communicated to trial participants in a timely manner (prior to the changes, if reasonably possible).

Personal data will only be processed for specified, explicit and legitimate purposes, and will be adequate, relevant and limited to those purposes. Data will be stored and transferred securely for all processing. The trial will undergo an information governance risk assessment at the CTRU to ensure its proposed processing is compliant with data protection laws.

Confidentiality of participant data will be maintained at all times, with access to data granted only to those who need it for legitimate reasons (i.e. to conduct the trial, or to ensure the trial has been conducted lawfully). Participants will allow access to their confidential data through the informed consent process. Copies of participants' consent forms, which will include participants' full names, will be collected when a participant is randomised into the trial by the CTRU. In addition, participant name and address may be collected for questionnaire-posting or email address/telephone number if the participant chooses to complete the questionnaires electronically. All other data collection forms that are transferred to or from the CTRU will be coded with a unique participant trial number and will include two participant identifiers, usually the participant's initials and date of birth. Data will be held securely on paper and electronically at the Clinical Trials Research Unit (CTRU). The CTRU will have access to the entire database for monitoring, co-ordinating, and analysis purposes.

Sites are responsible for maintaining this pseudonymisation on any data sent to the CTRU. Any exceptions (e.g. collecting unredacted consent forms at the CTRU for central monitoring of informed consent) will only be for legitimate reasons and will be explained fully to participants in advance of data processing. Where central monitoring of source documents, or copies of source documents, is required by CTRU, the participant's name must be obliterated by site before sending. Any breach of confidentiality or of participants' personal data will be handled and reported (if required) in line with relevant laws.

Data will be made available for secondary research once the main trial objectives are complete.

If a participant withdraws consent from further trial treatment and/or further collection of data, their data will remain on file and will be included in the final trial analysis.

Participant health data will also be obtained from the National Emergency Laparotomy Audit (NELA), a standard patient registry that is used by the NHS and held by NHS England and the Healthcare Quality Improvement Partnership (HQIP). This data will be collected for the purposes of the SWAT relating to the integration of routine data (see section 23.1) and will not be used for any other purpose. NELA have strict rules about sharing their data. You can find out more at https://www.nela.org.uk/NELA Privacy Policy. The data collected from NELA will be stored securely at the CTRU and will only be accessed by authorised members of the trial team. The data will be pseudonymised and will be linked using three participant identifiers (date of birth, NHS number and NELA ID).

